3.6.4.1 Subgroup Analysis of Laboratory Values

Subgroup summaries will be presented for the following summary tables. These summaries will be repeated for the Period 1 (Safety Analysis Set) and 12-month LEM exposure (On-Treatment Safety Analysis Set) separately.

- Mean and mean change from baseline by visit for selected parameters in [Table 7](#)
- TEMAVs

Table 7 Selected Laboratory Parameters for Subgroup Analysis

Category	Parameters
Hematology	hematocrit, hemoglobin, platelets, red blood cell count, and white blood cell count
Chemistry – Liver Function Tests	alanine aminotransferase, alkaline phosphatase, aspartate aminotransferase, gamma glutamyl transpeptidase, direct bilirubin, total bilirubin
Chemistry – Renal Function Tests	blood urea/blood urea nitrogen, creatinine

The following demographic and baseline information will be used in the subgroup summary:

- Age group 1 (<65, 65 to <75, and ≥ 75 years old)
- Age group 2 (<65 and ≥ 65 years old)
- Sex (male and female)
- Race (white, black, Asian, and other)
- Region (North America, Europe and New Zealand, Asia)
- BMI (<25, 25 to 30, >30 kg/m²)

3.6.5 Vital Signs

Descriptive statistics for vital signs parameters (ie, diastolic and systolic BP, pulse, respiration rate, temperature) and weight, and changes from Study Baseline and Period 2 Baseline will be presented by visit and treatment group. Analysis of changes from baseline will be based on the number of subjects with both nonmissing baseline and relevant postbaseline results.

Clinically notable vital sign values will be identified on the listings as those above (H) or below (L) a clinically notable range, as per [Table 8](#). The clinically notable vital sign values will be presented for change from Study Baseline (Safety Analysis Set) by treatment group and by time point. This will also be repeated for the 12-month LEM exposure (On-Treatment Safety Analysis Set), summarized by treatment group and duration of exposure.

Table 8 Vital Sign Criteria

Variable	Criterion Value ^a	Change Relative to Study Baseline/Period 2 Baseline ^a	Clinically Notable Range
Pulse rate	>120 bpm	Increase of 15 bpm	H
	<50 bpm	Decrease of ≥ 15 bpm	L
Systolic BP	>180 mmHg	Increase of ≥ 20 mmHg	H
	<90 mmHg	Decrease of ≥ 20 mmHg	L
Diastolic BP	>105 mmHg	Increase of ≥ 15 mmHg	H
	<50 mmHg	Decrease of ≥ 15 mmHg	L
Weight	-	Increase of $\geq 7\%$	H
	-	Decrease of $\geq 7\%$	L
Respiratory Rate	>30 bpm	Increase of ≥ 10 bpm	H
	<8 bpm	Decrease of ≥ 4 bpm	L

BP = blood pressure, H = high, L = low

a: Clinically notable means that a value must meet the criterion value and must attain the specified magnitude of change relative to Study Baseline or Period 2 Baseline, as appropriate.

3.6.6 Electrocardiograms

Descriptive statistics for ECG parameters and changes from Study Baseline (Safety Analysis Set) will be presented by treatment group. This will also be repeated for the 12-month LEM exposure (On-Treatment Safety Analysis Set), summarized by treatment group and duration of exposure. Shift tables will present changes from Study Baseline in ECG interpretation (categorized as normal; abnormal, not clinically significant; and abnormal, clinically significant) by time point.

In addition, maximum postbaseline measurement will also be tabulated separately for the Period 1 and 12-month LEM exposure by treatment group as follows:

- Number and percentage of subjects with QTcF of >450 msec, and >500 msec during the treatment
- Number and percentage of subjects with a QTcF increment of >30 msec, and >60 msec from the baseline visit.
- Number and percentage of subjects with PR of >220 msec
- Number and percentage of subjects with QRS of >120 msec

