9.7.1.1.4 EXPLORATORY ENDPOINTS

The following endpoints will be explored for LEM5 and LEM10. Except for PK endpoints, comparisons to PBO will be made.

- Change from Study Baseline in the mean value of the item on quality of sleep from the Sleep Diary for:
 - The 1st 7 mornings after the 1st dose in Period 1

- Months 1, 3, and 6
- Change from Study Baseline and Period 2 Baseline (as appropriate) in the mean value of the item on quality of sleep from the Sleep Diary for:
 - Subjects with 1, 3, 6, 9, and 12 months exposure (revised per Amendment 06)
- Change from Study Baseline in:
 - EQ-5D-3L at Months 1, 3, and 6
 - WPAI-GH at Months 3 and 6
- Change from Study Baseline and Period 2 Baseline (as appropriate) in:
 - EQ-5D-3L in subjects with 3, 6, 9, and 12 months exposure (revised per Amendment 06)
 - WPAI-GH in subjects with 3, 6, 9, and 12 months exposure (revised per Amendment 06)
- Number and percentage of subjects with a rating of a positive medication effect on each PGI-Insomnia item (1) at Months 1, 3, and 6 (placebo-controlled Treatment Period 1), and (2) with 3, 6, 9, and 12 months exposure (Treatment Period 1 and Treatment Period 2 combined) (revised per Amendment 06)
- Change from Study Baseline and Period 2 Baseline (as appropriate) of sSOL, sSE, sWASO, sTST with 1, 3, 6, 9, and 12 months exposure, and ISI and FSS with 3, 6, 9, and 12 months exposure. (revised per Amendment 06)
- Mean score on the T-BWSQ of LEM5, and LEM10 compared to PBO at End of Study
- Plasma concentrations of lemborexant and its metabolites M4, M9, and M10
- PK of lemborexant using population modeling
- Relationships between lemborexant PK, efficacy, and/or safety variables using PK/PD modeling

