9.7.1.6.3 EXPLORATORY EFFICACY AND PHARMACODYNAMIC ANALYSES

The change from Study Baseline for the mean score of the quality of sleep item on the Sleep Diary will be analyzed using MMRM, assuming MAR for the mean of the 1st 7 days of Period 1 and at Months 1, 3, and 6. (revised per Amendment 03)

Health-related quality of life: the change from Study Baseline for the EQ-5D-3L scores (both total score and Visual Analog Scale score), and the four scores from WPAI-GH will be using MMRM, assuming MAR for Month 1 (EQ-5D-3L only) and Months 3 and 6 (both EQ-5D-3L and WPAI-GH). (revised per Amendment 03)

Each item on the PGI-Insomnia at Months 1, 3, and 6 will be analyzed separately by calculating the number and percentages of subjects for each response category (eg, negative [3], neutral [2], positive [1] medication effect). The percentage of positive responses will be compared between treatment groups using the chi-square test, and repeated for age subgroups.

Summaries of all efficacy endpoints will be performed for 12 months exposure. Where appropriate, 95% CIs around the mean change from Study Baseline or Period 2 Baseline (for Period 1 and Period 2 data, respectively) will be presented. (revised per Amendment 06)

No multiplicity adjustment is planned for the exploratory and pharmacodynamic endpoints. (revised per Amendment 03)

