9.7.1.8.5 ELECTROCARDIOGRAMS

Descriptive statistics for ECG parameters and changes from Study Baseline (Safety Analysis Set) will be presented by treatment group and visit. This will also be repeated for the 12-month LEM exposure (On-Treatment Safety Analysis Set), summarized by treatment group and duration of exposure. (revised per Amendment 06)

Shift tables will present changes from Study Baseline in ECG interpretation (categorized as normal and abnormal) by time point. (revised per Amendment 03)

For each subject, the maximum observed QTcF, the corrected QT interval calculated using Bazett's formula (QTcB), and the maximum prolongation from Study Baseline in QTcF will be compiled. Categorical analyses of subjects (number and percent) with maximum observed QTcF values >450 ms, >480 ms, and >500 ms and maximum prolongations (from Study Baseline) in QTcF >30 ms and >60 ms will be presented by treatment group and by time point. Categorical analyses of subjects (number and percent) with maximum observed PR values >220 ms, and QRS values >120 ms will be presented by treatment group and by time point. This will also be repeated for the 12-month LEM exposure (On-Treatment Safety

Analysis Set), summarized by treatment group and duration of exposure. (revised per Amendment 06)

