3.7 Other Analyses

3.7.1 EQ-5D-3L

The EQ-5D-3L instrument comprises questions on 5 dimensions (mobility, self-care, usual activities, pain/discomfort and anxiety/depression) and a visual analogue score (EQ VAS). Each dimension has 3 levels: no problem, some problems, extreme problems and the EQ VAS is ranged from 0 ("Worst imaginable health state") to 100 ("Best imaginable health state").

Each dimension score will be summarized separately at Study Baseline and each postbaseline timepoint (Month 1, Month 3 and Month 6) using frequency count on observed data only with no imputation. The change from Study Baseline of EQ VAS will be summarized by treatment group for Month 1, Month 3, and Month 6. The change from Study Baseline of EQ VAS will be analyzed using MMRM assuming MAR for Month 1, Month 3 and Month 6 on observed data only based on FAS with no imputation for missing values.

The each dimension and EQ-VAS change from Study Baseline/Treatment Period 2 Baseline (as appropriate) will be summarized for the 12-month LEM exposure (On-Treatment Safety Analysis Set), summarized by treatment group and duration of exposure.

The time point window presented in [Section 6.2.3](#) will be used to determine the analysis visit.

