3.7.2.1 WPAI-GH

The WPAI-GH consists of six questions: Q1 = currently employed; Q2 = hours missed due to health problems; Q3 = hours missed other reasons; Q4 = hours actually worked; Q5 = degree health affected productivity while working; Q6 = degree health affected productivity in regular unpaid activities.

The four main outcomes derived by the following definition will be summarized by visit. The change from Study Baseline for the main outcomes will be summarized by visit. This will also be repeated for the 12-month LEM exposure (On-Treatment Safety Analysis Set), summarized by treatment group and duration of exposure.

The time point window presented in 8.2.4 will be used to determine the analysis visit.

1. Percent work time missed due to health: $Q2 / (Q2+Q4) * 100$
2. Percent impairment while working due to health: $Q5 / 10 * 100$
3. Percent overall work impairment due to health: $[\{Q2 / (Q2+Q4)\} + \{1 - (Q2 / (Q2+Q4))\} * (Q5/10)] * 100$
4. Percent activity impairment due to health: $Q6 / 10 * 100$

The above 1 to 3 will be obtained from the subjects who were employed (ie., Q1 = 'Y').

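### SAP 3.6.6 omits the protocol's >480 ms maximum-QTcF category, and SAP 3.7.2.1 names no model for WPAI-GH where the protocol and other SAP sections call for MMRM and a placebo comparison

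*SAP*

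**What the plan says.** **QTcF.** Protocol 9.7.1.8.5 asks for "Categorical analyses of subjects (number and percent) with maximum observed QTcF values >450 ms, >480 ms, and >500 ms" by treatment group, and repeats the analysis for 12-month lemborexant exposure. SAP 3.6.6 tabulates the maximum postbaseline value for the same two settings, with the first item being "Number and percentage of subjects with QTcF of >450 msec, and >500 msec during the treatment". The increments (>30 and >60 ms), PR >220 ms and QRS >120 ms match the protocol.

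**WPAI-GH.** Protocol 9.7.1.6.3 (and the synopsis) states that "the four scores from WPAI-GH will be using MMRM, assuming MAR for Month 1 (EQ-5D-3L only) and Months 3 and 6". WPAI-GH at Months 3 and 6 is an exploratory endpoint under protocol 9.7.1.1.4, which says "Except for PK endpoints, comparisons to PBO will be made"; SAP 3.1.3 repeats that sentence above the same endpoint. SAP 3.7.2.1 derives the four scores and then says "The change from Study Baseline for the main outcomes will be summarized by visit". It names no model, contrast or confidence interval.

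**The concern.** The SAP is the document from which the tables are programmed. If a protocol analysis is missing there and the change is not recorded, it will probably not be produced, and a reader of the report cannot tell a decision from an oversight.

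For QTcF, the loss is the number of subjects in the intermediate range, in both the placebo-controlled and the 12-month tables. A confirmed QTcF above 450 ms at Screening is an exclusion (criterion 15), so an on-study maximum above 480 ms would normally be a change from entry status.

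For WPAI-GH, a programmer who follows 3.7.2.1 literally would produce descriptive statistics by arm and no adjusted difference from placebo. The exploratory objective is framed as a comparison with placebo.

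**Working it through.** There is no plan figure to reproduce. The check is a comparison of texts.

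**1. QTcF thresholds.** Protocol {450, 480, 500} minus SAP {450, 500} leaves {480}. That is one missing row in each of two tabulations (Period 1 and 12-month exposure). The thresholds are cumulative, so a subject is counted as follows:

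| Subject's maximum QTcF | Rows under the protocol | Rows under the SAP |
|---|---|---|
| above 450, up to 480 ms | >450 | >450 |
| above 480, up to 500 ms | >450, >480 | >450 |
| above 500 ms | >450, >480, >500 | >450, >500 |

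The first two lines are identical under the SAP. Subtracting the >500 count from the >450 count gives the number above 450 and up to 500 ms, but nothing in the table splits that number at 480. The increment rows measure change from baseline and do not recover the absolute value.

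**2. WPAI-GH.** The protocol's model covers 4 scores × 2 visits × 2 doses = 16 contrasts with placebo. SAP 3.7.2.1 gives a method for none of them. Other SAP text bears on this as follows:

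- 3.1.3 still promises comparison with placebo for this endpoint.
- 3.3.5 sets MMRM under MAR as the default for continuous variables unless otherwise stated, and refers to Section 3.4 for details. WPAI-GH is not covered in Section 3.4.
- Comparable endpoints have their methods written out. For EQ VAS, 3.7.1 says "The change from Study Baseline of EQ VAS will be analyzed using MMRM assuming MAR for Month 1, Month 3 and Month 6"; PGI-Insomnia has a chi-square test (3.7.2); quality of sleep has an MMRM (3.8).

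Read together, 3.1.3 and 3.3.5 point to an MMRM compared with placebo, while the section dedicated to WPAI-GH points to summaries only.

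**3. Declaration.** SAP Section 5 lists two changes: extra MMRM time points for the primary and key secondary analyses, and the On-Treatment Safety Analysis Set. Neither covers the >480 ms row or the WPAI-GH method.

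**The case against.** Four objections deserve weight.

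- **The WPAI-GH model may survive by default.** SAP 3.3.5 supplies MMRM under MAR, 3.1.3 supplies the comparator, and 3.7.2.1 does not say that no model will be fitted. This stands to the extent that a reader who infers that the SAP has deleted the placebo comparison goes beyond the text. It does not settle the matter, because the default refers to a section that omits WPAI-GH.
- **The summaries are not useless.** SAP Section 3 reports n, mean and SD, so an unadjusted difference and interval could be worked out by hand. True, but that is not the model the protocol specifies, and it makes no use of Month 3 data from subjects missing at Month 6.
- **The QTcF loss is small.** The >450, >500 and increment rows remain, all safety analyses are descriptive, and the maximum is among the SAP's standard statistics. If QTcF is among the ECG parameters summarized, those tables show whether any windowed visit value exceeded 480 ms. This stands: what is lost is the count of subjects.
- **Section 5 claims only major changes.** This may explain its silence on one table row, but the difference from the protocol is still recorded nowhere in the SAP.

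Three further inferences are not supported. Silence in SAP Table 1 is not evidence of an undeclared departure, since that table records changes between SAP versions 1.0 and 2.0. No loss of precision for WPAI-GH can be calculated, because 3.7.2.1 plans no alternative test to set against the MMRM. An omission of QTcB is not clearly shown: the protocol only says it will be compiled, with no category, and the SAP promises descriptive statistics for ECG parameters without listing them.

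**Conclusion.** The QTcF discrepancy is clear from the two texts: one of three protocol thresholds is missing in both tabulations, undeclared. It is not a concealed safety signal, because every affected subject still appears in the >450 ms row.

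The WPAI-GH discrepancy is real but narrower. SAP 3.7.2.1 conflicts with protocol 9.7.1.6.3 and with the SAP's own 3.1.3 and 3.3.5. It is an inconsistency to resolve, and the documents do not show that the analysis was withdrawn.

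Both are limited in reach: one descriptive safety table and one exploratory endpoint with no multiplicity control. The Month 6 sSOL, sSE and sWASO tests are unaffected. The conclusion rests on no numerical assumption, only on reading 3.6.6 and 3.7.2.1 as what will be programmed; the separate table shells were not available.

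**What to change.** - **SAP 3.6.6:** add a >480 ms row to the maximum-QTcF tabulation for Period 1 and for 12-month exposure. State whether maximum QTcB is compiled; this is a minor clarification.
- **SAP 3.7.2.1:** specify an MMRM assuming MAR on the FAS, at Months 3 and 6, for each of the four scores, with the three work scores in employed subjects only. Terms: baseline score, region, age group, treatment, visit and treatment-by-visit. Report LEM5 and LEM10 differences from PBO with 95% CIs. Write the terms out, because the EQ VAS text in 3.7.1 lists no covariates to borrow.
- If either departure is intended, list it with its reason in SAP Section 5 instead.

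The cost is two table rows and one model specification applied to four scores. No new data are needed. The SAP's own rule in Section 1 is that modifications are approved before unblinding, so the edit belongs before the Period 1 unblinding.

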3.6.7 Other Safety Analyses

3.6.7.1 Columbia-Suicide Severity Rating Scale (C-SSRS)

Suicidality is assessed using a self-rated electronic version of the C-SSRS (eC-SSRS). The eC-SSRS assesses an individual's degree of suicidality, including both suicidal ideation and suicidal behavior. The occurrence of suicidal ideation or suicidal behavior at each visit will be summarized by treatment group using frequency count. A subject will be counted once for each of these categories if at least one question is answered positive belonging to the category.

In addition, self-injurious non-suicidal behavior will also be summarized separately for occurrence in a similar fashion to suicidal ideation and behavior.

3.6.7.2 Tyrer Benzodiazepine Withdrawal Symptom Questionnaire (T-BWSQ)

Withdrawal symptoms are assessed using the T-BWSQ at the End of Study (EOS) visit. Subjects are asked about the presence/absence and severity of the symptoms listed in the questionnaire. For each listed symptom, the subject is to respond "No" (Score = 0), "Yes – moderate" (Score = 1) or "Yes – severe" (Score = 2).

The sum of responses will be the subject's total score. The total score will be summarized by treatment group using descriptive statistics. In addition, the number and percentage of subjects with a total score of ≥ 3 will be summarized using frequency count. Since this questionnaire is completed at the EOS visit only, this analysis will be performed at the EOS visit based on Safety Analysis set. The same analysis will be repeated for the subgroup based on the duration of exposure.

3.7 Other Analyses

3.7.1 EQ-5D-3L

The EQ-5D-3L instrument comprises questions on 5 dimensions (mobility, self-care, usual activities, pain/discomfort and anxiety/depression) and a visual analogue score (EQ VAS). Each dimension has 3 levels: no problem, some problems, extreme problems and the EQ VAS is ranged from 0 ("Worst imaginable health state") to 100 ("Best imaginable health state").

Each dimension score will be summarized separately at Study Baseline and each postbaseline timepoint (Month 1, Month 3 and Month 6) using frequency count on observed data only with no imputation. The change from Study Baseline of EQ VAS will be summarized by treatment group for Month 1, Month 3, and Month 6. The change from Study Baseline of EQ VAS will be analyzed using MMRM assuming MAR for Month 1, Month 3 and Month 6 on observed data only based on FAS with no imputation for missing values.

The each dimension and EQ-VAS change from Study Baseline/Treatment Period 2 Baseline (as appropriate) will be summarized for the 12-month LEM exposure (On-Treatment Safety Analysis Set), summarized by treatment group and duration of exposure.

The time point window presented in [Section 6.2.3](#) will be used to determine the analysis visit.

3.7.2 Patient Global Impression (PGI) - Insomnia

The PGI-Insomnia questionnaire captures the global impression of the study medication's effect at each postbaseline time point. The PGI-Insomnia has 3 items related to study medication effect (helped/worsened sleep, decreased/increased time to fall asleep, and increased/decreased TST) on a 3-point scale (1=positive medication effect, 2=neutral medication effect, and 3=negative medication effect) and 1 item related to perceived appropriateness of study medication strength also on a 3-point scale (medication: 1=too strong, 2=just right, and 3=too weak).

Each item will be summarized separately as number and percentage of subjects for each time point (Month 1, Month 3 and Month 6). Furthermore, each item will be analyzed using chi-square test for Month 1, Month 3 and Month 6 on observed data only based on FAS with no imputation for missing values, and repeated for age subgroups. For this analysis, each item will be categorized as follows: "positive medication effect" versus others for the first 3 item; "just right" versus others for the last item). This will also be repeated for the 12-month LEM exposure (On-Treatment Safety Analysis Set) will be summarized by treatment group and duration of exposure.

The time point window presented in 8.2.3 will be used to determine the analysis visit.

3.7.2.1 WPAI-GH

The WPAI-GH consists of six questions: Q1 = currently employed; Q2 = hours missed due to health problems; Q3 = hours missed other reasons; Q4 = hours actually worked; Q5 = degree health affected productivity while working; Q6 = degree health affected productivity in regular unpaid activities.

The four main outcomes derived by the following definition will be summarized by visit. The change from Study Baseline for the main outcomes will be summarized by visit. This will also be repeated for the 12-month LEM exposure (On-Treatment Safety Analysis Set), summarized by treatment group and duration of exposure.

The time point window presented in 8.2.4 will be used to determine the analysis visit.

1. Percent work time missed due to health: $Q2 / (Q2+Q4) * 100$
2. Percent impairment while working due to health: $Q5 / 10 * 100$
3. Percent overall work impairment due to health: $[\{Q2 / (Q2+Q4)\} + \{1 - (Q2 / (Q2+Q4))\} * (Q5/10)] * 100$
4. Percent activity impairment due to health: $Q6 / 10 * 100$

The above 1 to 3 will be obtained from the subjects who were employed (ie., Q1 = 'Y').

3.8 Exploratory and Pharmacodynamic Analyses

The change from Study Baseline for the mean score of the quality of sleep item on the Sleep Diary will be analyzed using MMRM assuming MAR (no missing value imputation) for the mean of the 1st 7 days of Period 1 and at Months 1, through 6.

Furthermore, the mean score of the quality of sleep item change from Study Baseline/Treatment Period 2 Baseline (as appropriate) for the 12-month LEM exposure (On-Treatment Safety Analysis Set), summarized by treatment group and duration of exposure.

4 INTERIM ANALYSES

4.1 DSMB (Data Safety Monitoring Board)

The DSMB will serve as an independent safety monitoring committee and will perform the safety data reviews. The interim safety analyses will be conducted by an independent statistician, who is working on behalf of Eisai from a CRO that is independent of study conduct. To maintain the credibility and integrity of the trial, procedures will be implemented to ensure the DSMB and the independent statistician have sole access to the unblinded interim safety data. Full details of the DSMB operation procedures are documented in the DSMB charter. The sponsor will be kept blinded until the unblinding of Period 1. No decision to stop the study based on superior efficacy or futility of lemborexant to placebo is planned. Data will be cleaned as required prior to the scheduled DSMB data reviews.

